### **Methodology/ Protocol:**

Subjects will be recruited from the principal investigator's clinics as well as the Kirklin Clinic Urology clinic. Advertisements in the newspaper will also be used to recruit subjects. Patients will be screened using the OAB-q Short Form Questionnaire and the Medical, Epidemiological, and Social Aspects of Aging Questionnaire (MESA). Patients will qualify with any response of "Quite a bit" or greater on the OAB-q SF questionnaire. Stratified randomization will be based on the presence or absence of SUI as demonstrated on the MESA questionnaire. The subject will then undergo a physical examination and vaginal smear.

## Study Flow Diagram

Baseline measurements will include lab findings (dip urinalysis, vaginal pH, vaginal maturation index), pelvic organ prolapse quantification evaluation, subjective assessment of vaginal atrophy, a post-void residual volume and a 3-day bladder diary. Women with an intact uterus will undergo a pelvic ultrasound to assess endometrial thickness at baseline and after 12 weeks treatment with estradiol. If they do not receive estradiol treatment no follow-up ultrasound will be performed. Questionnaires include the Overactive Bladder Questionnaire (OAB-q), Pelvic Floor Distress Inventory (PFDI-20), Pelvic Floor Impact Questionnaire (PFIQ-7), Pelvic Organ Prolapse/Urinary Incontinence Sexual Function Questionnaire (PISQ-12) and the SF-12, a short form general health inventory.

Detrol LA will be prescribed with a 4 mg dose QD. Estrace vaginal cream (0.1 mg estradiol per gram) will be prescribed as 0.5 grams (a finger tip length of cream) to be

## Inclusion Criteria:

- Irritative voiding symptoms to include sensory urgency, frequency, urge incontinence, nocturia
- Postmenopausal women with a prior oophorectomy or 1 year from last menstrual period
- Women age 40 – 90
- \*Women with hysterectomy with preserved ovaries must be age 55 or greater or have a documented FSH > 40 (to ensure post-menopausal status)
- Community dwelling
- Ability to participate in a 12 month study
- ambulatory

## Exclusion Criteria:

- Post void residual > 150 ml
- Glaucoma without ophthalmologist clearance
- HRT in the past 6 months
- Current anticholinergic treatment
- Breast cancer
- Impaired mental status
- Undiagnosed vaginal bleeding in past 12 months
- endometrial thickness on pelvic ultrasound > 5 mm
- History of thromboembolic event
- Gynecologic cancer
- Untreated urinary tract infection (would be eligible after treatment)
- Stage III pelvic organ prolapse or greater
- Recent diuretic medication changes (one month from change)
- Neurologic condition affecting bladder function (Multiple Sclerosis, Parkinsons, spinal cord injury, spina bifida)
- congestive heart failure
- prior pelvic irradiation
- interstitial cystitis

applied into the vagina nightly for six weeks, then twice per week for the duration of the study (12 months).

All subjects will be called at 4 weeks to monitor for side effects and for possible drug dosage adjustment. This will be accomplished using a standardized evaluation tool.

Subjects will then be seen at 12 weeks (primary outcome visit) where a physical examination will be performed and the indices collected at baseline as well as the study questionnaires and bladder diary will be repeated. Participants that are not completely satisfied with the outcome of their current treatment regimen will be offered the opportunity to add the other therapy to their regimen. This will be determined using the Patient Satisfaction Questionnaire (PSQ) and the Patient Global Impression of Improvement (PGII). Women who were administered estradiol and have an intact uterus will undergo a pelvic ultrasound to document no change in endometrial thickness after 12 weeks of therapy.

All patients will be seen at 24 weeks for an additional physical examination to repeat baseline indices, as well as the study questionnaires and the 3-day bladder diary. Women with an intact uterus who chose to add estradiol to their treatment regimen after the 12 week visit, will undergo a pelvic ultrasound to document no change in endometrial thickness after 12 weeks of estradiol therapy.

Finally, at 52 weeks, patients will be asked to complete an additional 3-day bladder diary, repeat the questionnaires and report their long-term management choice for treatment of their urinary symptoms via US mail.

The ultimate measure of treatment success and likelihood of long-term compliance is intrinsically linked to the patient's perception of efficacy and symptom relief. Furthermore, it is difficult to measure objective improvement in a condition like OAB where symptoms are solely subjective. Thus, the primary study outcome to be measured is subjective patient improvement in irritative urinary symptoms. The measurement tool chosen is the Overactive Bladder Questionnaire (OAB-q). This instrument was chosen because it has been found to be a sensitive and reliable measure of subjective urinary symptom improvement with treatment. The OAB-q is a 33-item questionnaire that has a symptom bother scale as well as a health related quality of life scale that addresses coping, concern and worry, sleep and social interaction.

Changes in urinary frequency and incontinent episodes will be documented with a 3-day bladder diary. Assessment of the subjective (atrophy assessment) and the objective (pH, maturation index) vaginal environment will be conducted by a blinded clinician. Symptoms of voiding dysfunction and stress leakage will be collected with the validated questionnaires.

### **Statistics:**

Sample size calculation is based on a power ( $1 - \beta$ ) of 80% and an  $\alpha$  of 0.05. Comparison between the two groups on the validated Overactive Bladder Questionnaire (OAB-q) is the primary outcome and is, therefore, the basis of the sample size calculation. A standard deviation of 25 for this instrument was abstracted from the Coyne paper that measured the responsiveness of the instrument to anticholinergic therapy. We feel that a 20 point difference in outcome on this instrument would be clinically significant because, on average, 20 was associated with a reduction of 3 or more micturations per day. From these values and the proposed use of an independent t-test, 25 individuals per group were calculated. To this number, five patients per group were added to allow for attrition and intent to treat. Thus a total of 60 participants will be required to complete the study.

For the 2 groups of subjects who elect to crossover into combination therapy (i.e. Group 1 - estrogen with tolterodine added and Group 2 - tolterodine with estrogen added),

within group analyses will be performed using nonparametric testing because of the anticipated small number of subjects to crossover into combination therapy.

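### The only primary test named is an unadjusted t-test on an undefined OAB-q variable; an ANCOVA with baseline OAB-q and SUI stratum would protect power at almost no cost

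*Combined protocol and SAP*

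**What the plan says.** The Statistics section sets 80% power, alpha 0.05, an SD of 25 and a 20-point difference, and continues: "From these values and the proposed use of an independent t-test, 25 individuals per group were calculated". Five per group are added for attrition, giving 60. The only other analysis described is nonparametric within-group testing of women who add the second therapy. No covariate, model or stratum term is named.

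The primary variable is described in two ways. The methodology text after the Exclusion Criteria list says that "the primary study outcome to be measured is subjective patient improvement in irritative urinary symptoms". The Statistics section says "Comparison between the two groups on the validated Overactive Bladder Questionnaire (OAB-q) is the primary outcome". Neither states whether the analysed quantity is the 12-week score or the change from baseline. The instrument "has a symptom bother scale as well as a health related quality of life scale", and the plan does not say which of these is tested.

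The data for an adjusted analysis are already collected:

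- Baseline, under Study Flow Diagram: "Questionnaires include the Overactive Bladder Questionnaire (OAB-q".
- Week 12, the primary outcome visit: "the indices collected at baseline as well as the study questionnaires and bladder diary will be repeated".
- Stratification, under Methodology/ Protocol: "Stratified randomization will be based on the presence or absence of SUI as demonstrated on the MESA questionnaire".

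**The concern.** An unadjusted t-test uses baseline in one of two rigid ways. On 12-week scores it ignores baseline. On change scores it subtracts baseline with a slope fixed at 1. Which is more powerful depends on r: with equal SDs at the two visits, change is better when r exceeds 0.5 and the 12-week score is better below that. The plan neither gives r nor makes the choice. ANCOVA estimates the slope from the data, so it needs no guess.

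With about 25 evaluable women per arm, the wrong choice can cost 20 points of power or more. An undefined variable also leaves the analyst several possible primary tests once the data are in.

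The stratum term is a smaller matter. Stratifying on a prognostic factor balances the arms on it. A t-test that leaves the factor out then overstates the standard error and becomes conservative. The documents do not say whether SUI predicts the OAB-q.

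**Working it through.** **Inputs from the Statistics section.** SD 25, difference 20, alpha 0.05, power 80%, 25 per group. A two-sided test is assumed: it reproduces the stated figure, whereas a one-sided test gives about 20 per group.

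**The plan's own figure.** n = 2 × (25 × (1.960 + 0.842) / 20)² = 24.5, rounded up to 25 per group. It reproduces. Exact noncentral-t power at 25 per group (48 df) is 79.1%; at 30 per group it is 86.1%.

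**Assumptions not in the documents.** r = 0.2, 0.3, 0.5 or 0.7, and equal SDs at both visits. Under randomisation the expected arm difference is the same for 12-week scores and for change, so 20 points serves for both. Entry requires at least one response at a set level "or greater on the OAB-q SF questionnaire". This may narrow the baseline range and lower r.

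**Formulas.** Writing s for the SD of a score:

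- SD of change = s√(2(1 − r))
- ANCOVA residual SD = s√(1 − r²)
- ANCOVA uses 46 df (48 less one each for baseline and stratum), with variance inflated by 47/46 because the slope is estimated.

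**Case A: 25 is the SD of a score (s = 25).** The 12-week-score t-test has 79.1% power and a 95% CI half-width of 2.011 × 25 × √(2/25) = 14.2 points, whatever r is.

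| r | SD of change | t-test on change | ANCOVA residual SD | ANCOVA power | ANCOVA CI half-width |
|---|---|---|---|---|---|
| 0.2 | 31.62 | 59.1% | 24.49 | 79.8% | 14.1 |
| 0.3 | 29.58 | 64.9% | 23.85 | 81.9% | 13.7 |
| 0.5 | 25.00 | 79.1% | 21.65 | 88.5% | 12.5 |
| 0.7 | 19.36 | 94.7% | 17.85 | 97.0% | 10.3 |

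At r = 0 and 0.1 ANCOVA has 78.2% and 78.6%, against 79.1% for the 12-week-score t-test.

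**Case B: 25 is the SD of change.** Then s = 25/√(2(1 − r)) and the ANCOVA residual SD is 25√((1 + r)/2). The change-score t-test has 79.1% power throughout.

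| r | SD of score | t-test on 12-week score | ANCOVA residual SD | ANCOVA power |
|---|---|---|---|---|
| 0.2 | 19.76 | 93.9% | 19.36 | 94.2% |
| 0.3 | 21.13 | 90.6% | 20.16 | 92.5% |
| 0.5 | 25.00 | 79.1% | 21.65 | 88.5% |
| 0.7 | 32.27 | 57.4% | 23.05 | 84.4% |

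Simulation of 20,000 trials per setting, fitting arm, baseline and stratum, gave ANCOVA power of 80.3, 82.0, 88.7 and 96.9% in case A and 94.3, 92.5, 88.7 and 84.0% in case B. These agree with the formulas.

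**SUI stratum.** Simulation with balanced strata, r = 0 and total SD 25. The share of week-12 variance explained by SUI is assumed.

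| Share | t-test type I error | t-test power | ANCOVA type I error | ANCOVA power |
|---|---|---|---|---|
| 5% | 4.3% | 79.8% | 4.9% | 80.5% |
| 10% | 4.1% | 79.6% | 5.3% | 81.9% |
| 20% | 3.0% | 81.3% | 5.1% | 86.2% |

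**The case against.** The strongest reply is that nothing in the plan is wrong. The t-test is valid under randomisation, its sample size reproduces, and leaving out SUI errs on the safe side. Every gain quoted rests on an r that the documents do not give. In case A at r = 0.2 or below, ANCOVA gains essentially nothing over the 12-week-score test; at r = 0.7 it gains only about 2 points over the change-score test. All of this stands, and it is why the point is one of efficiency.

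It can also be said that the text leans towards change. The methodology speaks of improvement, the SD is taken from a paper described as measuring responsiveness to anticholinergic therapy, and the 20 points are tied to a reduction in micturitions. That narrows the ambiguity but does not define the variable. On that reading (case B, change-score test) ANCOVA's gain is 5 to 15 points: 84.4% to 94.2% against 79.1%.

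Using 25 per arm assumes the attrition allowance is fully spent. With all 30 per arm evaluable, the case A comparison is 86.1% for the 12-week-score t-test against 86.9, 88.6 and 93.6% for ANCOVA at r = 0.2, 0.3 and 0.5. The gains shrink but keep their direction.

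The variance shares for SUI have no basis in the documents, and at 5% or 10% the power gain is only 1 to 2 points. The case for the stratum term is mainly that the analysis should follow the randomisation.

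Finally, the t-test is only proposed, within a sample-size sentence, so an adjusted analysis is not ruled out. But if that sentence does not fix the primary analysis, nothing in the plan does.

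**Conclusion.** The concern holds, as an efficiency and specification point that should be addressed. The plan names an unadjusted t-test, does not define what it is applied to, and uses neither the baseline OAB-q nor the stratification factor.

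With 25 per arm and a 20-point difference, either form of t-test can fall below 60% power, depending on an unstated correlation and on what the SD of 25 describes. Over the same range ANCOVA stays between about 80% and 97%. It gains about 9 points over both t-tests at r = 0.5 and gives up about 1 point at most, when r is near 0. Most of the gain comes from the baseline score.

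These figures assume a two-sided test, equal SDs at both visits and r from 0.2 to 0.7. No error in the sample size and no bias in the treatment comparison is claimed.

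**What to change.** Add to the Statistics section wording such as:

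> The primary analysis is an ANCOVA of the 12-week score on [symptom bother or health-related quality of life: the scale on which the sample size was based], with terms for randomised arm, baseline score on the same scale, and SUI stratum (present or absent). The adjusted difference between arms is reported with its 95% confidence interval. An independent t-test on the same scale, on [12-week scores or change from baseline], is a sensitivity analysis.

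The sponsor should fill both brackets before any outcome data by arm are examined, and should state whether 25 is the SD of a score or of a change.

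The cost is two or three sentences and two degrees of freedom (48 to 46 with 25 per arm). No new patients, visits or measurements are needed, and the sample size stays at 60.

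### The planned unadjusted t-test is valid but gives up precision: the primary OAB-q comparison should adjust for baseline score and SUI stratum, on one named scale

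*Combined protocol and SAP*

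**What the plan says.** The Statistics section makes the between-group comparison on the OAB-q the primary outcome. It takes 80% power, alpha 0.05, an SD of 25 and a 20-point difference, and concludes: "From these values and the proposed use of an independent t-test, 25 individuals per group were calculated". It then enlarges the groups ("To this number, five patients per group were added to allow for attrition and intent to treat") and closes with "Thus a total of 60 participants will be required to complete the study".

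Three other places bear on the analysis:

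- **Stratification**, under Methodology/Protocol: "Stratified randomization will be based on the presence or absence of SUI as demonstrated on the MESA questionnaire".
- **Baseline measurement**, under Study Flow Diagram: "Questionnaires include the Overactive Bladder Questionnaire (OAB-q"). At the 12-week primary outcome visit, described after the exclusion list, "the indices collected at baseline as well as the study questionnaires and bladder diary will be repeated".
- **Outcome**, in the text justifying the choice of instrument: "the primary study outcome to be measured is subjective patient improvement in irritative urinary symptoms". The same text says that the OAB-q has a symptom bother scale and a health-related quality-of-life scale, and does not choose between them.

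No covariate or stratum adjustment is described anywhere. The only other analysis given is nonparametric within-group testing of women who add the second therapy.

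**The concern.** A baseline measure of the primary outcome is usually its best predictor, and the plan collects one. It also stratifies the randomisation on SUI, presumably because SUI was expected to matter for outcome. The named test takes no account of the stratum. How it treats baseline is not stated: if week-12 scores are compared, baseline is left out; if changes are compared, baseline enters only by subtraction, which is generally less efficient than regression on it.

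The plan also leaves open which scale is primary, whether the score or the change is tested, and which of these the SD of 25 describes. Until that is settled, the power of the planned test cannot be pinned down. At stake are the width of the interval for the arm difference and the freedom to choose the scale and variable after the data are seen. The validity of the test is not at stake.

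**Working it through.** **Inputs from the Statistics section.** SD 25, difference 20, alpha 0.05, power 80%, 25 per group plus 5. Sidedness is not stated; two-sided is taken because a one-sided calculation gives 20 or 21 per group, not 25.

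**Assumptions of this review.** Correlation r between baseline and week-12 score of 0.3 to 0.7; the documents give none. Where a score SD is converted to a change SD or back, equal SDs at the two visits are also assumed.

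**1. The plan's own figure.** n = 2 × 25² × (1.960 + 0.842)² / 20² = 24.5, so 25 per group. The exact t calculation gives 25.5, so 26. Total: 2 × (25 + 5) = 60. Both stated figures reproduce.

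**2. Power of the unadjusted test for 20 points** (noncentral t, 2n − 2 degrees of freedom). With 25 per arm it is 79.1% (80.7% by normal approximation). With 30 per arm it is 86.1%.

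**3. Power with adjustment** (2n − 4 degrees of freedom, for baseline and stratum; any gain from the stratum itself is not counted).

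- Case A, 25 is the SD of a score: residual SD = 25 × √(1 − r²).
- Case B, 25 is the SD of change: residual SD = 25 × √((1 + r)/2).

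| Case | r | Residual SD | Power, 25 per arm | Power, 30 per arm |
|---|---|---|---|---|
| Unadjusted | – | 25.00 | 79.1% | 86.1% |
| A | 0.3 | 23.85 | 82.7% | 89.1% |
| A | 0.5 | 21.65 | 89.2% | 94.0% |
| A | 0.7 | 17.85 | 97.2% | 98.9% |
| B | 0.3 | 20.16 | 93.0% | 96.5% |
| B | 0.5 | 21.65 | 89.2% | 94.0% |
| B | 0.7 | 23.05 | 85.2% | 91.0% |

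A simulation of Case A with both covariates in the model (20,000 runs) agreed to within about half a percentage point: 82.2%, 88.7% and 96.8% at 25 per arm; 88.4%, 93.6% and 99.0% at 30.

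**4. Width of the 95% CI at 30 per arm.** Unadjusted, ± 12.9 points. Adjusted in Case A, ± 12.3, 11.2 and 9.2 points at r = 0.3, 0.5 and 0.7.

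**5. If the SD of 25 does not belong to the variable tested** (unadjusted).

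- 25 is a score SD but change is tested: SD = 25 × √(2(1 − r)).
- 25 is a change SD but the week-12 score is tested: SD = 25 / √(2(1 − r)).

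| Mismatch | r | SD | Power, 25 per arm | Power, 30 per arm |
|---|---|---|---|---|
| Change tested | 0.3 | 29.6 | 65% | 73% |
| Change tested | 0.7 | 19.4 | 95% | 98% |
| Score tested | 0.3 | 21.1 | 91% | 95% |
| Score tested | 0.7 | 32.3 | 57% | 66% |

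At r = 0.5 the two SDs coincide and nothing changes. The range is therefore 57-95% at 25 per arm and 66-98% at 30, on both sides of the plan.

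**6. Cost if baseline predicts nothing (r = 0).** The difference detectable with 80% power moves from 20.22 to 20.24 points at 25 per arm, and from 18.39 to 18.40 at 30.

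**The case against.** The strongest reply is that nothing here is wrong. The sample size reproduces. An unadjusted t-test is valid, and after stratified randomisation it is usually conservative. The gain from adjustment depends on a correlation that no document supplies. If change is the tested variable, as the word improvement suggests, baseline is already used in part. All of this stands. It limits the point to efficiency and specification, but does not remove it: the data are collected anyway, and adjustment costs almost nothing even if r is zero.

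Three stronger readings are tempting and should be resisted.

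- **That 60 must finish, so 72 must be randomised** (60 ÷ (25/30) = 72). The sentence just before the total says that the allowance is already included, and the closing phrase can mean the number needed to carry out the study. This is a matter of wording, not a shortfall.
- **That the 20-point difference has no justification.** A clinical-importance reason is given: "on average, 20 was associated with a reduction of 3 or more micturations per day". A target difference need not be the expected one, and the view that this anchor describes change within patients would rest on a cited paper that is not available here.
- **That the trial is underpowered, with power as low as 57%.** That figure combines the unfavourable mismatch, r = 0.7 and loss of the whole allowance. The same formulas give up to 95% at that sample size. The 79% against the planned 80% is only exact t against normal approximation.

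**Conclusion.** The point holds as a modest recommendation that should be adopted. There is no arithmetic error: 25 per group and 60 in total are sound. The named primary analysis is valid but ignores the SUI stratum and uses baseline at most by subtraction. The primary scale and the tested variable are not fixed.

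Adjustment adds about 4 to 18 percentage points of power for 20 points at 25 per arm in Case A (79% to 83-97%), and about 6 to 14 in Case B (79% to 85-93%). With all 60 analysed, the gains are 3 to 13 points in Case A and 5 to 10 in Case B. These sizes rest on the assumed correlations, and in Case B on equal SDs at both visits. Selection on OAB-q Short Form responses at screening might narrow the baseline spread and so disturb that equality. The direction of the recommendation depends on neither, because the loss when baseline is uninformative is about 0.02 points.

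**What to change.** 1. Name one OAB-q scale as primary, and state whether the SD of 25 is that of a score or of a change on that scale.
2. Replace the independent t-test as the primary analysis with:

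> Week-12 scores on that scale will be compared between randomised arms by linear regression adjusted for baseline score and SUI stratum, reporting the arm difference with its 95% CI.

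3. As a minor clarification of wording, state that 60 women will be randomised, 30 per arm, and that the unadjusted t-test has 86% power for 20 points if all are analysed and 79% (exact calculation) if five per arm are lost.

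The change needs no extra patients, visits or data. It costs two degrees of freedom and slightly more analysis work. It should be made before the outcome data are examined.

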#### Secondary

1. To determine if patients with subjectively unsatisfactory results with monotherapy (tolterodine or estrogen cream) receive further improvement in OAB symptoms with a change to combination therapy (tolterodine plus estrogen).
2. To compare symptom specific and general quality of life and patient satisfaction measures in women treated with oral anti-muscarinic therapy versus those treated with intra-vaginal estrogen versus those treated with both.
3. To describe any change in urinary frequency or leakage in the treatment groups on a 3-day bladder diary.
4. To describe any association of symptom improvement with changes in vaginal epithelial maturation assessment.
5. To compare voiding and post micturition symptoms including slow stream, hesitancy, straining, terminal dribble, and feeling of incomplete emptying in the treatment groups.
6. To correlate observed changes in symptoms of stress incontinence in the women in each treatment group.

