### **Relevance:**

Lower urinary tract bladder storage symptoms include urinary frequency, urinary urgency, nocturia and urge incontinence. Overactive bladder syndrome is a condition in which urgency is the predominant symptom with or without urge incontinence and is usually accompanied by frequency and nocturia, as defined by the International Continence Society. These are distressing problems that have a major impact on quality of life. Prevalence of overactive bladder symptoms in women in the United States has been estimated to be 16-17%, and this prevalence increases with age.

The mainstay of treatment of women with OAB syndrome is pharmacotherapy with anticholinergic agents, as well as behavioral therapy. Anticholinergic agents are thought to exert their effect via antagonism of the muscarinic receptors of the detrusor muscle, thus blocking transmission of the parasympathetic nervous system with subsequent reduction in detrusor muscle contraction. This method of treatment has demonstrated a 60% response rate as reported in the Cochrane Database of Systemic Reviews. In addition to anticholinergic therapy, vaginal atrophy is often corrected as part of a pharmacologic treatment plan.

Vaginal atrophy is a condition that is vastly prevalent in post-menopausal women. It is thought to affect up to 48% of post-menopausal women. Many women with this condition experience vaginal dryness, irritation, dyspareunia, as well as urinary symptoms including

dysuria, urgency, frequency, nocturia, incontinence and recurrent urinary tract infections. Often these symptoms are dismissed as “nuisance” symptoms and treatment of atrophy is not initiated. With the waning levels of estrogen in the post-menopausal period the lower genital and urinary tracts experience thinning of the epithelium, loss of rugation, and reduced secretions. Atrophy results in elevated vaginal pH, changes in the usual urogenital flora, an increased risk of urinary tract infections, as well as loss of maturation of the vaginal epithelial cells.

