### **Research Design:**

The study design is a randomized controlled intent to treat trial where postmenopausal women seeking care for symptoms suggestive of OAB (urgency, frequency, urge incontinence, nocturia) would be randomized to treatment with Detrol LA in study arm #1, versus treatment with local estradiol vaginal cream (Estrace, *Warner Chilcott, Rockaway, NJ*) in study arm #2. After screening for inclusion and exclusion criteria (see list below) women would be randomly assigned to a treatment group. After 12 weeks of treatment the subjects who are not completely satisfied with the results of their current therapy will be offered the opportunity to add the other therapy to their treatment regimen (see study flow diagram below). All subjects will be followed for 52 weeks. In addition to being analyzed as part of their original randomized arm, patients who receive dual therapy will be sub-analyzed for further improvement in their OAB symptoms.

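### Secondary aim 1 asks one question about all women who add the second drug, but the Statistics section analyses them only as two small groups, with no combined estimate

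*Combined protocol and SAP*

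**What the plan says.** Secondary aim 1 is a single question covering both starting drugs: "To determine if patients with subjectively unsatisfactory results with monotherapy (tolterodine or estrogen cream) receive further improvement in OAB symptoms" after a change to the combination. The Research Design section likewise treats these women as one set: "patients who receive dual therapy will be sub-analyzed for further improvement in their OAB symptoms".

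The only analysis text for them is the last paragraph of Statistics. It defines two groups by first drug, "Group 1 - estrogen with tolterodine added and Group 2 - tolterodine with estrogen added", and then states that "within group analyses will be performed using nonparametric testing because of the anticipated small number of subjects to crossover into combination therapy". It does not name the test or its sidedness, give an expected number of women, or plan a combined analysis, an effect estimate or an interval. The 0.05 level and 80% power in that section belong to the primary comparison.

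**The concern.** The plan expects few women to add the second drug and then divides those few, although the aim does not ask for the division. Each result then rests on part of the relevant data. If one group shows a significant change and the other does not, nothing in the plan says whether aim 1 has been met. The report could rest on whichever group looks better, or on two inconclusive tests where a combined estimate would have been informative. At stake are the precision and clarity of the answer to a secondary aim. The primary comparison is not affected.

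**Working it through.** **1. The plan's own sample size.** Inputs from Statistics: SD 25 ("A standard deviation of 25 for this instrument was abstracted"), difference 20 points ("We feel that a 20 point difference in outcome on this instrument would be clinically significant"), alpha 0.05, power 80%.

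- Two-sided: n = 2 × (1.960 + 0.842)² × (25/20)² = 24.5, so 25 per group, as stated. Solving with the t distribution gives 25.5, so 26, which is close enough.
- One-sided: 2 × (1.645 + 0.842)² × (25/20)² = 19.3, so 20, which does not match.

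Alpha is therefore read as two-sided. Adding 5 per group gives 30 per arm and 60 in total. No corresponding figure exists for the add-on analysis.

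**2. Smallest attainable p-value.** For the exact two-sided signed-rank test, the minimum p with n women is 2/2ⁿ: 0.125 at n=4, 0.0625 at n=5, 0.031 at n=6. With 5 or fewer women, p<0.05 cannot be reached even if every woman improves. Two groups of 5 combined (n=10) could reach 0.002.

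**3. How likely is a group of 5 or fewer?** The documents give no add-on rate. The binomial probability, over a range of assumed rates, is:

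| Assumed add-on rate | 25 per arm | 30 per arm |
|---|---|---|
| 10% | 97% | 93% |
| 20% | 62% | 43% |
| 30% | 19% | 8% |
| 40% | 3% | 0.6% |
| 50% | 0.2% | 0.02% |

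The only response figure in the documents is in Relevance: "This method of treatment has demonstrated a 60% response rate", for anticholinergics. If the other 40% in both arms added therapy, which is an assumption, there would be 10 to 12 women per group (0.40 × 25 to 0.40 × 30).

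**4. Power, split against combined.** Exact two-sided signed-rank test, 40,000 simulated trials, normally distributed changes, the same mean change in both groups. The standardised changes of 0.5 and 0.8 are assumptions. With p the power in one group, the chance that at least one of two independent groups is significant is 1 − (1 − p)².

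| Change | Women per group | One named group | At least one of two | Combined |
|---|---|---|---|---|
| 0.8 SD | 8 | 43% | 1 − 0.571² = 67% | 82% (n=16) |
| 0.8 SD | 12 | 66% | 1 − 0.336² = 89% | 95% (n=24) |
| 0.5 SD | 8 | 19% | 1 − 0.806² = 35% | 43% (n=16) |
| 0.5 SD | 12 | 31% | 1 − 0.688² = 53% | 63% (n=24) |

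If both groups had to be significant, power at 0.8 SD with 8 per group would be 0.429² = 18%. The plan does not say which rule applies.

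**5. Interval width, which needs no assumed effect.** In units of the SD of change, the 95% half-width is t/√n. For 8 women it is 2.365/√8 = 0.84. For 16 women stratified by arm (14 degrees of freedom) it is 2.145/√16 = 0.54.

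**6. Error rate if either group may carry the aim.** The exact test is discrete, so its attained size s lies below 0.05, and the chance of at least one false positive is 1 − (1 − s)².

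- n=6: s = 2/64 = 0.031, giving 6.2%.
- n=8: s = 10/256 = 0.039, giving 7.7%.
- n=12: s = 174/4096 = 0.042, giving 8.3%.

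The rate does not rise steadily with n. The highest value between 6 and 12 women is at n=10: s = 50/1024 = 0.049, giving 9.5%.

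**The case against.** **The split is defensible.** One group adds tolterodine and the other adds estrogen, in women dissatisfied with different drugs. A combined mean averages two different additions, with weights set by who opts in. This stands, and it is why the group results should be kept. It does not justify leaving out the combined estimate that aim 1 describes.

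**A combined look is not excluded.** The Research Design sentence mentions no split, so a reader might wrongly infer that the plan rules out pooling. It does not. The two sections are unreconciled, and the only stated analysis is by group.

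**Significance is not shown to be impossible.** A reader might infer from step 2 that the planned tests must fail. The documents say only that numbers will be small, and the offer goes to every woman not completely satisfied. At an add-on rate of 40%, a group of 5 or fewer is unlikely. The test is also unnamed: at n=5 a one-sided exact test can reach 0.031, and the uncorrected normal approximation, unreliable at that size, gives 0.043.

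**One group's power is not the fair comparator.** Setting 43% against 82% overstates the loss if either group may carry the aim. The like-for-like comparison at 8 per group is 67% against 82%, and at 12 per group the gap is 6 points (0.8 SD) or 10 points (0.5 SD). This is accepted.

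**The false-positive inflation is smaller than the textbook figure.** A reader might quote 1 − 0.95² = 9.75%. The exact test does not attain 0.05 at these sizes, and the plan never says that one significant group would establish the aim.

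**Conclusion.** The point holds as a mismatch between aim and analysis. Aim 1 and Research Design pose one question, while Statistics answers it only in two parts, without a combined estimate or a decision rule. Some precision is lost at any group size. At 8 women per group and an assumed 0.8 SD change, power is about 67% for at least one group against 82% combined, and the interval half-width is 0.84 SD against 0.54 SD. These figures assume similar numbers and a similar mean change in the two groups. The claim that p<0.05 cannot be reached is confined to an exact two-sided test with 5 or fewer women, and the documents do not predict that number.

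A stronger inference, that pooling would let the trial show a benefit of the added drug, is not supported. These women are selected for dissatisfaction at week 12 and have no concurrent control. A more precise before-after change is still only a before-after change. This is an inexpensive improvement to a secondary analysis.

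**What to change.** Add to the last paragraph of Statistics that the analysis for secondary aim 1 is one paired analysis of the change in OAB-q from week 12 to week 24 in all women who add the second drug, stratified by original arm (a stratified signed-rank test, or a paired model with an arm term), reported with a 95% confidence interval. Name the test and its sidedness. Keep the Group 1 and Group 2 results beside it, each with its own interval and no separate significance claim. State that the result describes change and is not evidence of a drug effect.

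The cost is a sentence or two. No new data are needed, because the questionnaires are already repeated at weeks 12 and 24. The downside is that the combined figure averages two different additions, so the two group estimates must stay visible.
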